[figure not shown]

Figure EE-1. Cost-effectiveness plane for differences in costs versus differences in QALYs for CLI in comparison with DBS

[figure not shown]

Figure EE-2. Probability of CLI being cost-effective in comparison with DBS at different levels of willingness to pay per QALY

Supplementary information

Appendix I — Possible protocol deviations and violations

Deviations

Usage of other DBS devices

e.g., usage of material from other manufacturer than Medtronic for DBS material. Although usage of material from Medtronic was described in the protocol, usage of material from other manufacturers was not expected to have a significant effect on treatment efficacy. Furthermore, the study protocol emphasized that treatments were to be given according to usual care.

Usage of other routes of CLI administration

e.g., if it proved not possible to construct a percutaneous endoscopic gastrostomy (PEG), a percutaneous radiological gastrostomy (PRG) was considered a feasible alternative by the treating physician. In line with the previous paragraph, this was deemed not to have a significant impact on treatment effect but the risk for AEs may be altered.

Missing of visits at two weeks, three, six or nine months

Since primary outcomes all were based on the assessment from the 12-month follow-up visit, missing of interim visits, although undesirable, was deemed not to have a significant impact on analyses.

Completing baseline visit after initiation of treatment (in ancillary patient preference observational arms)

During the course of the study, sometimes it proved challenging to contact patients and receive all mail-in CRFs patients had to fill in, prior to initiation of therapy in participating centers other than the primary center. If the baseline assessments were completed within reasonable time after initiation of therapy (*i.e.*, less than two weeks), it was estimated that these patients were still able to report the situation prior to therapy (as requested).

Failure to initiate follow-up after signing informed consent (in ancillary patient preference observational arms)

In case it proved impossible to plan and complete the baseline visit and subsequent visits due to logistic reasons after signing informed consent, this resulted in failure of study participation. Since the missing patients would have been at random, this probably had no influence on the integrity of analyses and was therefore marked as deviation from the protocol.

Violations

Refusal of allocated treatment

Since DBS treatment through usual care was restricted with a long waiting list, it was expected that some patients hoped to receive this treatment sooner through study participation. It was an anticipated unwanted scenario that some patients therefore would decline allocated treatment after randomization, because of a strong preference for the other treatment. This would be considered a protocol violation and made patients ineligible for the modified intention to treat population.

[figure not shown]
Missing of 12-month follow-up visit

Missing the 12-month visit would have resulted in significant incompleteness of data. Since this would probably not have been at random, this could have affected integrity of analyses. Therefore, this visit was deemed indispensable and missing it was considered a protocol violation.

Migration from the RCT to ancillary patient preference observational study population

If a patient found participation in the RCT too burdensome after receiving allocated treatment, continuation of study participation was encouraged. If a patient crossed-over to the ancillary patient preference arm, this was deemed a violation from the RCT protocol.

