5. TREATMENT OF SUBJECTS

5.1 Investigational product/treatment

CLI and DBS are both complex treatments and are therefore performed by teams that consist of various specialties (e.g. neurologist, neurosurgeon, gastroenterologist, and specialized nurses). In the Netherlands, 6 centres are permitted to perform DBS. Three of these also offer CLI, but in a much smaller number. CLI is performed in approximately 45 centres. For the study, CLI and DBS treatments should be optimally performed, i.e. by the best-trained teams. It is inevitable that the centres that perform the treatments at present perform the study-treatments as well. This implies that CLI and DBS will be carried-out in different centres. An advantage of this (Dutch) situation is that the study design closely resembles the current clinical practice, and as such the study results will be highly externally valid.

DBS treatment (Medtronic, Minneapolis, MN, USA)

Treatment is in accordance with the usual care regarding this procedure. For DBS, a neurosurgeon places two electrodes in the brain. These are connected to an implantable pulse generator. Patients are on average 4 days hospitalized. Patients do not receive PD drugs on the day of surgery until the end of the procedure. A stereotactic technique will be employed for implantation with the Leksell stereotactic frame (Elekta, Stockholm, Sweden) and guided by MRI. For this part of the surgery, patients will have local or general anaesthesia, both methods are possible in usual care and the surgeon will decide the method with the patient. The decision for electrode placement is based on MRI, microelectrode recordings and macro-electrode stimulation effects. A four contact electrode will be implanted in the subthalamic nucleus (STN). Subsequently, patients will have a second surgery under general anaesthesia to implant the pulse generator (ActivaPC or ActivaSC), subcutaneously in the subclavian area. The electrodes are connected to the pulse generator. During the course of the study, changes in drug treatment are allowed. Patients will regularly visit the outpatient clinic to adjust stimulation parameters and PD medication while assessing the interaction between both treatments.

CLI treatment (Duodopa, Abbott, Abbott Park, IL, USA)

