Adherence to the intervention CLI treatment was defined as having the percutaneous endoscopic gastrostomy (PEG) tube placed and having continuous administration of levodopa by means of the CLI pump. Adherence to the intervention DBS treatment was defined as having the DBS system implanted and turned on. Study patients were able to make small adjustments to their CLI or DBS settings if permitted by their healthcare professionals, major changes to treatment regimens could only have been implemented by healthcare professionals. Therefore, adherence was expected to be very good. Continuation of treatment was regularly inquired during the planned visits.

Protocol deviations were quantified and projected per study group. Protocol deviations were defined as treatment, research activities or other procedures that diverged from the study protocol were considered to have had no significant consequences for interpretation of study outcomes. A protocol violation was defined as a divergence from the protocol that might significantly have impacted the completeness, accuracy, and/or reliability of the study data, was not in line with the consent form, or

might have impacted patients' safety, welfare or rights.^{16,17} In Appendix I possible protocol deviations and violations were elucidated. All protocol deviations were line-listed according to treatment group. In addition, the number and percentage of patients in each treatment group experiencing one or more protocol deviations were presented. Minor protocol deviations did not impact inclusion in all analyses. Protocol violations did not alter inclusion in the (modified) intention-to-treat analysis or the ancillary patient preference observational analyses and resulted in exclusion from the per protocol analysis.

Patient replacement and missing data

Main clinical outcome

For participants with missing values for the main clinical outcome (PDQ-39), three approaches were used:

I - In case only the 12-month follow-up PDQ-39 was missing and the 9-month PDQ-39 was present, the latter was used, minus or plus the mean difference in PDQ-39 between nine and 12 months follow-up for that treatment arm (of present data), since little change in PDQ-39 between nine and 12 months follow-up was expected.

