CLI: continuous intrajejunal levodopa infusion, DBS: deep brain stimulation, RCT: randomized controlled trial, SAE: serious adverse event

Ancillary patient preference observational study arms

For both the observational CLI and DBS groups, changes in outcomes from baseline to 12 months after start of treatment were displayed in Table SAP4. The numbers of patients who stopped their advanced treatment and who switched between advanced treatments were reported.

To assess the extent of external validity of the mITT population, differences in baseline characteristics of all randomized patients (*i.e.*, both the CLI and DBS groups combined) and the separate observational (*i.e.*, non-randomized) CLI group and DBS group of the ancillary patient preference study were shown with 95% CI in supplementary Table SAP1-S. With regard to the main clinical outcome (the change in PDQ-39 summary index scores at 12 months relative to baseline), the difference between patients randomized to CLI treatment (mITT population) and those who preferred that treatment was reported with 95% CI. The same was done for patients randomized to DBS treatment (mITT population) and those who preferred that treatment. These figures were presented in the text.

To assess the impact of the treatment on the change in PDQ-39 at 12 months relative to baseline with more power, this was analyzed using multivariable regression in the total group of patients (*i.e.*, both the mITT randomized population and non-randomized population), taking into account significant imbalanced baseline variables and participation in the RCT or preference observational study.

Table SAP4. Ancillary patient preference observational study arms, outcomes at 12 months.

Outcome	Baseline				Within-treatment Change from Baseline to 12 Months			
	CLI		DBS		CLI		DBS	
	no. of patients	mean±SE	no. of patients	mean±SE	no. of patients	mean±SE or n (%)	no. of patients	mean±SE or n (%)
Main clinical outcome PDQ-39 summary index score								
Secondary outcomes LEDD (mg per day) ALDS score in on-phase								

ALDS: Amsterdam Linear Disability Scale, CLI: continuous intrajejunal levodopa infusion, DBS: deep brain stimulation, LEDD: Levodopa Equivalent Daily Dose, PD-CRS: Parkinson's Disease Cognitive Rating Scale, PDQ-39: Parkinson's Disease Questionnaire-39, SE: standard error. For continuous variables, mean and Standard Error were reported, for dichotomous variables the number of patients (n) and percentage (%).

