The primary health outcome in the cost-effectiveness analysis was the change in the PDQ-39 between baseline and 12 months after randomization. The change score showed the increase or decrease in number of difficulties across eight different dimensions of health (including mobility, activities of daily living, emotional well-being, and stigma) as experienced by patients in the preceding month. Dimension scores are coded on a scale of 0 (perfect health as assessed by the measure) to 100 (worst health as assessed by the measure). The change score was defined as the mean score on the eight scales at month 12 minus the mean score at baseline, in theory ranging from -100 to +100 with a score of 0 representing 'no change'.

The primary health outcome in the cost-utility analysis was the number of QALYs. Patient's health status was assessed with the EQ-5D-3L at baseline, one week, three months, six months, nine months, and 12 months post randomization. The EQ-5D contained five items: mobility, self-care, usual activities, pain/complaints, and mood (anxiety/depression).³¹ Each item had three response options: no problems, some problems, or serious problems. EQ-5D scoring profiles at successive measurements were converted into health utility scores using general population based tariffs of time trade-off ratings of health states.³² QALYs were calculated by taking the product sum of the health utility scores during follow-up and the interval lengths in years in-between successive measurements.

Health economic analysis methods

Analysis population

The CEA and CUA were done with the modified intention-to-treat population (see page 9) with references to the CONSORT-flow diagram in Figure SAP-1 and the baseline characteristics of the two RCT-subpopulations in Table EE1. Summary statistics for health utility scores at baseline were included in the manuscript text.

Cost-effectiveness threshold

The applied cost-effectiveness threshold for the sample size calculation was €120,000 as described and substantiated in the published study protocol.¹

Statistical decision rules

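### Preference-arm PDQ-39 baselines recalled after treatment start (less than two weeks) stay in the external-validity and pooled analyses, and no sensitivity analysis leaves them out

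*SAP*

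**What the plan says.** SAP Appendix I lists late completion of the baseline visit in the preference arms among the deviations, not the violations. Contacting patients and getting mailed forms back had sometimes been difficult "prior to initiation of therapy in participating centers other than the primary center". The rule is: "If the baseline assessments were completed within reasonable time after initiation of therapy", with reasonable time glossed as "less than two weeks", the visit is accepted, because "it was estimated that these patients were still able to report the situation prior to therapy (as requested".

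Three other parts of the SAP determine what happens to these patients:

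- **Inclusion.** Under Adherence and protocol deviations and violations: "Minor protocol deviations did not impact inclusion in all analyses". The same section says that even violations leave inclusion in the ancillary analyses unchanged. The definition of the ancillary population (Analysis populations) asks for a baseline visit and a follow-up visit, but not that the baseline precede treatment.
- **Use.** Under Ancillary patient preference observational study arms, the change in PDQ-39 from this baseline fills Table SAP4. It is compared between randomised and preference patients within each treatment, and it enters a pooled regression whose purpose is "To assess the impact of the treatment on the change in PDQ-39 at 12 months relative to baseline with more power". That regression takes account of significantly imbalanced baseline variables and of participation in the RCT or the preference study.
- **Instrument.** HEAP, Health outcomes, describes the PDQ-39 as covering difficulties "as experienced by patients in the preceding month".

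In the RCT, Protocol 7.3 places the baseline before randomisation and hence before treatment.

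**The concern.** The SAP synopsis says the preference arms serve primarily to judge how far the RCT results generalise. That judgement rests on comparing change from baseline between two cohorts, and the cohorts do not share a baseline definition: one is always assessed before treatment, the other sometimes from memory afterwards.

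A patient describing the previous state just after an operation, or after infusion has begun, may recall it differently. The interval overlaps the admission (Protocol 5.1: about 4 days for DBS, 5 to 12 days for CLI). The direction cannot be predicted. Higher PDQ-39 scores are worse, so early benefit that colours the recalled baseline would shrink the apparent improvement, and peri-procedural burden would enlarge it.

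The cohort is not small. On the planning numbers in Protocol 4.4, preference patients make up 180/(180+66) = 73% of the pooled set, or 120/(120+66) = 65% on the lower estimate. Protocol 12.6 adds that preference-group outcomes gain interest if the RCT efficiency results are indecisive. No planned analysis shows what the late baselines do to the results; the SAP's sensitivity analyses concern the randomised populations.

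**Working it through.** **1. The plan's own figures.** Protocol 4.4 gives detectable PDQ-39 differences for preference versus randomised patients (SD 15, two-sided 5%, 80% power, two-group t-test). All reproduce with the noncentral t distribution and 33 randomised patients per arm:

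| Comparison | n | Stated | Recomputed |
|---|---|---|---|
| DBS, 180 preference patients | 33 v 108 | 8.4 | 8.42 |
| DBS, 120 preference patients | 33 v 72 | 8.9 | 8.92 |
| CLI, 180 preference patients | 33 v 72 | 8.9 | 8.92 |
| CLI, 120 preference patients | 33 v 48 | 9.6 | 9.62 |

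**2. Overlap with the recall period.** Answered literally for a 30-day month on day 13, the last day inside the limit, 13/30 = 43% of the period falls after treatment start. This is a ceiling, because patients were asked about the time before therapy.

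**3. Bias in one arm's mean change.** Let f be the share of the arm with late baselines and b their mean baseline shift. The bias is f × b. Neither input is in the documents; the ranges are assumptions.

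| f | b = 2 | b = 5 | b = 8 | b = 10 |
|---|---|---|---|---|
| 10% | 0.2 | 0.5 | 0.8 | 1.0 |
| 20% | 0.4 | 1.0 | 1.6 | 2.0 |
| 30% | 0.6 | 1.5 | 2.4 | 3.0 |
| 50% | 1.0 | 2.5 | 4.0 | 5.0 |

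The bias reaches 1.6 points (the SAP's minimal clinically important difference, under Patient replacement and missing data) at f = 1.6/b: 80%, 32%, 20% and 16% for b = 2, 5, 8 and 10.

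**4. Effect on the randomised-versus-preference comparison.** With SE = 15 × √(1/n₁ + 1/n₂), the SE is 2.98 (33 v 108), 3.15 (33 v 72) and 3.39 (33 v 48). If the true difference is zero, the chance that the 95% CI excludes zero is Φ(bias/SE − 1.96) + Φ(−bias/SE − 1.96). A bias of 1.6 gives 8.4%, 8.0% and 7.6%, against 5%. A bias of 4 gives 26.8%, 24.5% and 21.8%. This applies the protocol's SD of 15 to change scores.

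**5. Effect on the pooled regression.** With treatment and participation as the only terms, the bias in the treatment coefficient is w × (CLI shift − DBS shift), where w = W_pref/(W_pref + W_RCT) and each W = n_CLI × n_DBS/(n_CLI + n_DBS).

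- RCT 26 + 26 (after 20% dropout), preference 72 + 108: W = 13 and 43.2, so w = 43.2/56.2 = 0.77.
- RCT 33 + 33, preference 48 + 72: W = 16.5 and 28.8, so w = 28.8/45.3 = 0.64.

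An equal shift in both preference arms gives zero bias; the participation term absorbs it. A 1.5-point shift in CLI only gives 1.5 × 0.77 = 1.15 points in the first case.

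**6. Precision without late baselines.** By the normal formula 15 × (1.96 + 0.84) × √(1/n₁ + 1/n₂), dropping 20% of the preference patients moves the detectable difference from 8.4 to 8.6 (33 v 86), 8.8 to 9.2 (33 v 58) and 9.5 to 10.0 (33 v 38).

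**The case against.** The strongest reply is that Appendix I records patients being asked about their state before therapy. A reader might infer that the baseline measures the treated state and that the change score is therefore wrong for these patients. The text does not support that: it shows short retrospective recall, with no evidence on size or sign. The 43% overlap likewise holds only if patients ignored the request.

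Second, deviations are already line-listed by treatment group, with the number and percentage of patients having any deviation. This stands: occurrence is largely covered. A listing does not show the effect on the results, and no listing of days after treatment start is specified.

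Third, a reader might infer that late baselines must be unequal by arm, since "CLI is performed in approximately 45 centres" and DBS in 6. Those are national counts, not counts of participating centres, so imbalance is possible rather than shown. The participation term then protects the pooled coefficient unless imbalance exists. It does not protect the randomised-versus-preference comparison.

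Fourth, a reader might conclude that these patients should be left out by default. That is debatable. At 30% late, about 22 of 72 CLI or 32 of 108 DBS patients would go, all from non-primary centres. The cohort would tilt towards the primary centre, against the purpose of the arms. Nor does the recall argument about the PDQ-39 carry over to recorded medication.

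Finally, the effect may be small. A 20% share with a 5-point shift gives 1.0 point, below 1.6 and far below the detectable 8.4 to 9.6. The preference results are also reported with confidence intervals and without individual P-values. This limits the weight of the point but does not answer it, because the share is not stated.

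**Conclusion.** The concern holds as a possible, untested recall bias in ancillary analyses. It bears directly on Table SAP4 and on the randomised-versus-preference differences. It bears on the pooled treatment coefficient only if the share or the shift of late baselines differs between CLI and DBS, in which case about 64 to 77% of the difference passes through, provided treatment and participation are the only terms.

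The illustrative 0.2 to 5.0 points per arm rests wholly on assumed shares and shifts. What the documents establish is the acceptance rule, the continued inclusion, and the lack of any analysis without these patients. The rule covers the preference arms only, so the randomised mITT comparison and the economic outcomes are unaffected. This is a cheap improvement to the plan, not a threat to the main results.

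**What to change.** Keep the planned analyses as the main ones and add to SAP, Ancillary patient preference observational study arms:

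1. Report, by arm, the number of patients whose baseline PDQ-39 is dated after treatment start, and the timing in days.
2. As a prespecified sensitivity analysis, repeat Table SAP4, the two randomised-versus-preference differences and the pooled regression without those patients.
3. If the results differ from the main ones, qualify the external-validity conclusion.

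The cost is a few lines of SAP wording, one date filter agreed before database lock, and a little extra analysis. Precision is slightly lower in the sensitivity analysis only: with 20% dropped, the detectable difference rises by about 0.2 to 0.5 points. The main analyses lose no patients.

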Appendix II — Flowchart ancillary patient preference observational study

Appendix III — Supplementary statistical analysis tables

Table SAP1-S. Baseline characteristics – RCT mITT population and ancillary patient preference observational study arms

	RCT all – all randomized patients (CLI or DBS)	Observational CLI – patients chose CLI treatment	Observational DBS – patients chose DBS treatment	Difference RCT all vs observational CLI difference (95% CI)	Difference RCT all vs observational DBS difference (95% CI)
Age (years)	n	n	n		
Sex, F (%)					
Time since PD diagnosis (years)					
Hoehn and Yahr stage in on-drug state (%)					
- Stage 1					
- Stage 1,5					
- Stage 2					
- Stage 2,5					
- Stage 3					
- Stage 4					
Levodopa-equivalent daily dose (mg/day)					
Level of experience of treating center with CLI and DBS treatment (%)*					
- Experienced in CLI, not in DBS					
- Experienced in DBS, not in CLI					
- Experienced in both CLI and DBS					
- Little experience in both CLI and DBS					

CLI: continuous intrajejunal levodopa infusion, DBS: deep brain stimulation, F: female, MDS-UPDRS: Movement Disorder Society's Unified Parkinson's Disease Rating Scale, mg: milligrams, NA: not available, PD: Parkinson's disease, RCT: randomized controlled trial

*Experienced in CLI/DBS: ≥ 5 patients treated per year in the two years previous to including the patient with the respective treatment in the treating center. A center may have changed in level of experience over time.

For normally distributed data, mean and standard deviation were presented, for non-normally distributed data median and interquartile ranges. For dichotomous variables, the percentage stated.

